----------------------	--

INVESTIGATOR STUDY ELIGIBILITY VERIFICATION FORM

Patient Name: (Network sites use subject initials) :

Medical Record No.: (Network sites use subject ID) :

Title: A Phase I/IIb Study of DEC205mAb-NY-ESO-1 Fusion Protein (CDX-1401) Given with Adjuvant Poly-ICLC in Combination with INCB024360 for Patients in Remission with Epithelial Ovarian, Fallopian Tube, or Primary Peritoneal Carcinoma Whose Tumors Express NY-ESO-1 or LAGE-1 Antigen

INCLUSION CRITERIA				
Yes	No	N/A	All answers must be "YES" or "N/A" for patient enrollment.	Date
			1. Eligible patients will be women with epithelial ovarian, fallopian tube, or primary peritoneal carcinoma after chemotherapy with no evidence of disease or minimal residual disease for primary or recurrent disease. This may or may not be measurable. These patients would normally enter a period of observation after standard management.	
			2. Any HLA type. (Historic HLA typing is permitted.)	
			3. Tumor expression of NY-ESO-1 or LAGE-1 by IHC and/or RTPCR.	
			4. Life expectancy > 6 months.	
			5. Hematology and biochemistry laboratory results within the limits normally expected for the patient population, without evidence of major organ failure. Have the following clinical laboratory values: 
• ANC \geq 1,000/μL• PLT \geq 100,000/μL• Hgb \geq 8 g/dL• Total bilirubin \leq 1.5 x ULN• Serum aspartate aminotransferase (SGOT/AST) or serum alanine aminotransferase (SGPT/ALT) \leq 3 x ULN• Serum creatinine \leq 2 x ULN	
			6. Have been informed of other treatment options.	
			7. Age \geq 18 years of age.	

INCLUSION CRITERIA				
Yes	No	N/A	All answers must be "YES" or "N/A" for patient enrollment.	Date

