			8. Patient or legal representative must understand the investigational nature of this study and sign an Independent Ethics Committee/Institutional Review Board approved written informed consent form prior to receiving any study related procedure.	
			9. Have an ECOG Performance Status of \leq 2. Refer to Appendix A .	
			10. The ability to swallow and retain oral medication.	
			11. Patients of child-bearing potential must agree to use acceptable contraceptive methods (e.g., double barrier) during treatment.	
			12. Patients may have received previous NY-ESO-1 vaccine therapy. Patients who received maintenance paclitaxel or bevacizumab are eligible for enrollment provided they have discontinued therapy (at least 4 weeks for prior taxane or prior bevacizumab) prior to randomization and recovered from toxicities to less than Grade 2.	

Investigator Signature: _____

Date: _____

INVESTIGATOR STUDY ELIGIBILITY VERIFICATION FORM

Patient Name: (Network sites use subject initials) :

Medical Record No.: (Network sites use subject ID) :

Title: A Phase I/IIb Study of DEC205mAb-NY-ESO-1 Fusion Protein (CDX-1401) Given with Adjuvant Poly-ICLC in Combination with INCB024360 for Patients in Remission with Epithelial Ovarian, Fallopian Tube, or Primary Peritoneal Carcinoma Whose Tumors Express NY-ESO-1 or LAGE-1 Antigen

EXCLUSION CRITERIA				
Yes	No	N/A	All answers must be "No" or "N/A" for patient enrollment.	Date
			1. Metastatic disease to the central nervous system for which other therapeutic options, including radiotherapy, may be available.	
			2. Other serious illnesses (e.g., serious infections requiring antibiotics, bleeding disorders).	
			3. History of severe autoimmune disorders requiring use of steroids or other immunosuppressives.	

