1.6.2.4 INCB024360 Clinical Studies

INCB24360-101 has been evaluated in Phase I study conducted by Incyte Corporation in subjects with refractory solid tumors. The study has used a 3+3 dose escalation design, with doses of INCB024360 ranging from 50 mg once daily (QD) to 700 mg twice daily (BID). Three subjects have initiated treatment at 50 mg QD, 4 subjects at 50 mg BID, 3 subjects at 100 mg BID, 6 subjects at 300 mg BID, 11 subjects at 400 mg BID, 5 subjects at 500 mg BID and 4 subjects at 700 mg BID.

INCB024360 has generally been well tolerated. The most common Grade 1 or Grade 2 AEs in $\geq 20\%$ reported have been fatigue, nausea, decreased appetite, vomiting, constipation, abdominal pain, diarrhea, dyspnea, back pain, and cough. The most common Grade 3 or Grade 4 AEs were

abdominal pain, hypokalemia, and fatigue (9.6% each). Despite 1 patient reporting a dose-limiting toxicity (DLT) of radiation pneumonitis at 300 mg BID, additional subjects were enrolled at this dose and no additional DLTs were reported. At 400 mg BID, 1 patient reported a DLT of Grade 3 fatigue, with no additional DLTs at this dose level. Another patient at 400 mg BID developed asymptomatic and transient hypopituitarism after 1 cycle of therapy and was able to continue dosing with INCB024360. Among the 18 subjects treated at either 600 mg or 700 mg BID, no DLTs were observed. Dose escalation was completed based on preliminary pharmacokinetic and pharmacodynamic data, which demonstrated that doses of INCB024360 above 300 mg BID achieved exposures exceeding the IC90 determined in nonclinical models and, in pharmacodynamic assays, reached a plateau for Kyn/Trp levels and ratios. In the final cohort of 600 mg BID, the effect of food on INCB024360 absorption was evaluated. No objective responses were reported. At 2 months, stable disease was seen in 15 patients and lasted \geq 4 months in 7 patients. The main AE reported in subjects receiving more than 2 cycles of INCB024360 has been Grade 1 or Grade 2 fatigue.

In a combination study conducted by Incyte Corporation of INCB024360 and ipilimumab in metastatic melanoma patients, 5 of 7 subjects enrolled at a dose of 300 mg BID of INCB024360 plus 3 mg/kg of ipilimumab, developed Grade 3 or Grade 4 AST and ALT elevations between 2 and 4 cycles of treatment. Only one of these subjects had a bilirubin elevation of Grade 1.

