4.2 Exclusion Criteria

Patients will be excluded from this study for the following:

1. Metastatic disease to the central nervous system for which other therapeutic options, including radiotherapy, may be available.
2. Other serious illnesses (e.g., serious infections requiring antibiotics, bleeding disorders).
3. History of severe autoimmune disorders requiring use of steroids or other immunosuppressives.
4. Concomitant systemic treatment with chronic use (based on the investigator's judgment) of corticosteroids, anti-histamine or non-steroidal anti-inflammatory drugs, and other platelet inhibitory agents (See also **Section 6.4** for restrictions/recommendations on ancillary therapy).
5. Chemotherapy, radiation therapy, or immunotherapy within 4 weeks prior to first dosing of study drug (6 weeks for nitrosoureas). Concomitant hormonal therapies for breast cancers are allowed.
6. Subjects being treated with a monoamine oxidase inhibitor (MAOI), or drug which has significant MAOI activity (e.g., meperidine, linezolid, methylene blue) within 3 weeks prior to screening.
7. Subjects who are currently receiving therapy with a potent CYP3A4 inducer or inhibitor (e.g. clarithromycin, telithromycin, nefazodone, itraconazole, ketoconazole, atazanavir).
8. Use of UGT1A9 inhibitor including: diclofenac, imipramine, and ketoconazole.
9. Participation in any other clinical trial involving another investigational agent within 4 weeks prior to first dosing of study drug.
10. Known hepatitis B, hepatitis C, or HIV.

11. Mental impairment that may compromise the ability to give informed consent and comply with the requirements of the study.
12. Lack of availability of a patient for immunological and clinical follow-up assessment.
13. Evidence of current drug or alcohol abuse or psychiatric impairment, which in the Investigator's opinion will prevent completion of the protocol therapy or follow-up.
14. Pregnant or nursing female patients.
15. Unwilling or unable to follow protocol requirements.
16. Any condition which in the Investigator's opinion deems the patient an unsuitable candidate to receive study drug (i.e., any significant medical illness or abnormal laboratory finding that would, in the investigator's judgment, increase the patient's risk by participating in this study).
17. Known hypersensitivity to any of the study drugs that will be given to the participant
18. Additional exclusion criteria for exploratory cohort ONLY: Known pulmonary hypertension.

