- Febrile neutropenia with standard of care treatment for \geq 7 days. Growth factors may be used according to American Society of Clinical Oncology guidelines.
- Platelets \leq 50 \times 10⁹/L
- Grade 3 or greater non-hematologic toxicity
- Serum bilirubin $>$ 3.0 mg/dL
- AST / ALT $>$ 3.5 x ULN
 - AST normal range: 15 U/L – 46 U/L
 - ALT normal range: 11 U/L - 66 U/L
- Serum creatinine $>$ grade 3 (equal or greater) will be considered a DLT
- Grade 3 or greater hypersensitivity reaction. If the hypersensitivity reaction is determined to be related to INCBO24360 alone, the INCBO24360 will be discontinued and patient may continue on treatment with CDX-1401 with Poly-ICLC at the discretion of the investigator.

Dose modification for exploratory cohort with Sirolimus (Roswell site ONLY):

Based on the completed trial (I 191511 “A Phase 1 Clinical Trial of mTOR Inhibition With Rapamycin for Enhancing Intranodal Dendritic Cell Vaccine Induced anti-Tumor Immunity In Patients with NY-ESO-1 Expressing Solid Tumors”), the 4 mg/day Sirolimus dose was safely used in combination with DEC205 and therefore dose modification is not expected. However, in the event of an unexpected toxicity attributed to Sirolimus, a lower dose of Sirolimus may be considered.

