- AST / ALT $> 3.5 \times \text{ULN}$
 - AST normal range: 15 U/L – 46 U/L
 - ALT normal range: 11 U/L - 66 U/L
- Serum creatinine $\geq \text{grade 3 (equal or greater)}$ will be considered a DLT
- Grade 3 or greater hypersensitivity reaction. If the hypersensitivity reaction is determined to be related to INCB024360 alone, the INCB024360 will be discontinued and patient may continue on treatment with CDX-1401 with Poly-ICLC at the discretion of the investigator.

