Urinary Pregnancy Test in Females of Childbearing Potential	X																							
Concomitant Medications	X ¹²	X			X		X		X		X		X		X		X		X		X			
Adverse Events	X	X			X		X		X		X		X		X		X		X		X			

Study Event	Baseline ¹	Cycle 1			Cycle 2		Cycle 3		Cycle 4		Cycle 5		Cycle 6		Cycle 7		.1.1 Treatment discontinuation ¹³	3 Months, 6 Months, and 12 Months After Last Vaccine or dose of INCB
		Day 1	Day 2	Day 15	Day 1 ± 3 days	Day 2												

- 1 To be performed within 28 days prior to the first vaccination.
- 2 Positive by either PCR or immunohistochemistry ((archived tissue (**Appendix F**) and/or frozen/fresh tumor tissue (**Appendix G**)). Documented historical NY ESO 1 positive results by IHC **or** PCR **or** serum antibody reactive with ESO are acceptable.
- 3 Refer to **Appendix H**
- 4 Including CT scan abdomen and pelvis, or PET/CT as described in **Section 8.5**; within 28 days prior to first vaccination. If patient early terms, CT will be performed at the PI's discretion.
- 5 Only 3 months and 6 month for those patients who have not experienced disease progression.
- 6 Hematology includes: CBC with auto differential, platelets. PT/INR for patients on anticoagulants.
- 7 Chemistry includes: glucose, urea nitrogen, creatinine, calcium, protein, albumin, bilirubin, AST, ALT, LDH, alkaline phosphatase.
- 8 Pharmacokinetic sampling is dependent upon cohort. Refer to **Section 7.7** for details.
- 9 Tumor markers to be obtained as per standard of care.
- 10 INCB024360 will be administered daily for 7 cycles.
- 11 Refer to **Section 7.5**.
- 12 Medications ongoing within 1 week prior to first dose of study drug.
- 13 Approximately 30 days after last study drug, con meds and AE's will be followed. Telephone contact is allowed.

Table 4 Schedule of Procedures/Observations (Exploratory cohort with Sirolimus-Roswell site ONLY)

Study Event	Baseline ¹	Cycle 1				Cycle 2				Cycle 3				Cycle 4				Cycle 5				^{1,2} Treatment discontinuation ¹²	3 Months, 6 Months, and 12 Months After Last Vaccine or dose of Sirolimus
		Day 1	Day 2	Day 15	Day 1 ± 3 days	Day 2	Day 1 ± 3 days	Day 2	Day 1 ± 3 days	Day 2	Day 1 ± 3 days	Day 2	Day 1 ± 3 days	Day 2	Day 1 ± 3 days	Day 2	Day 1 ± 3 days	Day 2	Day 1 ± 3 days	Day 2			
Informed Consent	X																						
Medical History	X	X		X	X		X		X		X		X		X		X		X		X		
Physical Examination, vital signs and weight	X	X		X	X		X		X		X		X		X		X		X		X		
NY-ESO-1, TIL, PD-L1, and/or LAGE-1 Expression in Tumor Tissue²	X																						

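### Inclusion 5 joins AST and ALT with 'or', so its numeric limit is met when only one enzyme is at or below 3 x ULN

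*Combined protocol and SAP*

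**What the plan says.** Inclusion 5 has a general opening sentence and a list of laboratory limits. The opening asks for "Hematology and biochemistry laboratory results within the limits normally expected for the patient population" and no sign of major organ failure. The transaminase line in the list reads "Serum aspartate aminotransferase (SGOT/AST) or serum alanine aminotransferase (SGPT/ALT") at or below 3 x ULN. The wording is the same in the Investigator Study Eligibility Verification Form and in section 4.1.

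Both enzymes are measured at baseline. Table 3, footnote 7 reads: "Chemistry includes: glucose, urea nitrogen, creatinine, calcium, protein, albumin, bilirubin, AST, ALT, LDH, alkaline phosphatase".

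Two other entry criteria could catch a raised enzyme:

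- Inclusion 12 requires patients to have "recovered from toxicities to less than Grade 2", but this is attached to those who had maintenance paclitaxel or bevacizumab.
- Exclusion 16 lets the investigator exclude for "any significant medical illness or abnormal laboratory finding that would" raise the patient's risk.

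On treatment, sections 6.3 (Phase IIb dose modification) and 6.3.1 (DLT) both list AST or ALT above 3.5 x ULN. Section 6.3 prints it as "AST / ALT $>$ 3.5 x ULN". Both sections also print the normal ranges, with upper limits of 46 U/L for AST and 66 U/L for ALT (for example "ALT normal range: 11 U/L - 66 U/L").

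**The concern.** With 'or', the transaminase line fails only when both enzymes exceed 3 x ULN. With 'and', it would fail when either does. A patient can therefore satisfy the numeric item with one enzyme already beyond the level that the protocol treats as toxicity once dosing has begun.

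What is at stake is attribution. Both uses of the 3.5 x ULN level require a treatment-related toxicity, and section 9.1.1.4 counts a pre-existing condition as an adverse event only if it gets worse. If the baseline is already above the level, crossing it no longer carries information, and the investigator has to judge whether a further rise is due to the drug.

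The liver is a reasonable organ to watch with this agent, although the signal is limited. Section 1.6.2.4 reports that 5 of 7 patients given INCB024360 300 mg BID with ipilimumab "developed Grade 3 or Grade 4 AST and ALT elevations between 2 and 4 cycles of treatment". Ipilimumab is not part of this trial, and the same section describes INCB024360 as generally well tolerated.

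The literal wording also matters for conduct. The form is a yes/no checklist. Appendix J says that no eligibility exceptions are granted and that patients enrolled with significant deviations from the criteria are removed. Two clinical sites are named in section 11.1. If one reads the line as 'either' and the other as 'each', the same patient could be eligible at one and a deviation at the other.

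**Working it through.** The plan states no figure to reproduce here. The check is a reading of the criteria, followed by simple arithmetic on the printed ranges.

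**1. Is there another numeric AST or ALT entry limit?** I went through all the inclusion and exclusion criteria in the form and in sections 4.1 and 4.2.

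| Clause | What it limits | States an AST or ALT value? |
|---|---|---|
| Inclusion 5, opening sentence | Results in the expected range, no major organ failure | No |
| Inclusion 5, transaminase line | One enzyme or the other at or below 3 x ULN | Yes, met by either enzyme |
| Inclusion 5, bilirubin line | Bilirubin at or below 1.5 x ULN | No |
| Inclusion 12 | Residual toxicity below Grade 2 after maintenance paclitaxel or bevacizumab | No |
| Exclusion 10 | Known hepatitis B, hepatitis C or HIV | No |
| Exclusion 16 | Abnormal findings, by investigator judgment | No |

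The transaminase line is the only one with a number.

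**2. Levels in U/L.** Inputs: upper limits AST 46 and ALT 66 (sections 6.3 and 6.3.1), entry multiple 3 (Inclusion 5), toxicity multiple 3.5 (sections 6.3 and 6.3.1). Level = multiple x upper limit.

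| | AST | ALT |
|---|---|---|
| Entry limit | 3 x 46 = 138 | 3 x 66 = 198 |
| Toxicity level | 3.5 x 46 = 161 | 3.5 x 66 = 231 |
| Gap between them | 161 - 138 = 23 | 231 - 198 = 33 |

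**3. Patients who meet the line under 'or'.**

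- AST 92, ALT 264: 92/46 = 2.0 and 264/66 = 4.0. The line is met through AST. ALT is 264 - 231 = 33 U/L above its toxicity level.
- Mirror case, ALT 132, AST 184: 132/66 = 2.0 and 184/46 = 4.0. The line is met through ALT. AST is 184 - 161 = 23 U/L above its toxicity level.

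These are hypothetical values. They test the numeric line only, not the general clauses.

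**4. The same line under 'each'.** Both patients fail. The highest values allowed are AST 138 and ALT 198 U/L, which lie 23 and 33 U/L below the toxicity levels.

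**5. Who is exposed.** In Phase IIb, Table 1 gives INCB024360 only to Cohort 2b, 25 of the 50 patients. This is the number receiving the drug, not the number expected to enter with one raised enzyme, which the documents do not allow one to estimate.

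**The case against.** The strongest reply is that Inclusion 5 is a single criterion with a single tick box, and its opening sentence is mandatory. A woman in remission with ALT at 4 x ULN may well fail that sentence whatever the transaminase line says. Other criteria deal with common causes of a raised enzyme: the bilirubin limit, the viral hepatitis exclusion, the exclusion for current drug or alcohol abuse, and the 4-week washout from chemotherapy, radiation and immunotherapy. 'Or' may also be shorthand, since sections 6.3 and 6.3.1 write one joint AST / ALT threshold and a site could read the entry line in the same way. Because both enzymes are measured at baseline, a later rise can be compared with a known value. Finally, the Phase I safety review has already selected 300 mg BID, so the dose decision that a misattributed DLT could have distorted is past.

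Most of this stands, and it is why the point ranks low. The general clauses probably exclude most such patients, nothing shows that anyone was enrolled on the permissive reading, and Phase IIb dose modification is now the main use of the threshold. But none of these clauses states an enzyme level. Numeric limits are there so that entry does not rest on judgment, and this one leaves the second enzyme to judgment. 'Or' cannot be explained by only one enzyme being available, because the panel contains both. If 'each' was always intended, the correction costs nothing and removes the doubt.

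**Conclusion.** The concern holds. As written, the only numeric AST/ALT entry limit can be met with one enzyme already above the protocol's own 3.5 x ULN toxicity level; in the two worked cases the excess is 33 U/L for ALT and 23 U/L for AST. This rests on the literal reading of 'or' and, for the U/L figures, on applying the ranges printed in the toxicity sections to the entry criterion, which prints none. No frequency is claimed. The effect is confined to patient safety and the attribution of later liver enzyme rises. It is a low-severity correction, worth making because it is so cheap, and it should rank below any point that touches the endpoint, the analysis or the dose.

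**What to change.** In the eligibility form and in section 4.1, change the line to: AST and ALT each at or below 3 x ULN. The 3.5 x ULN level in sections 6.3 and 6.3.1 can stay, because nobody who meets the reworded line is above it on the date of the baseline test. The assurance goes no further than that date, since baseline tests may be done up to 28 days before the first vaccination (Table 3, footnote 1).

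The cost is a short wording amendment in two places, with no new tests. The downside is that a rare patient with one raised enzyme, whom an investigator might otherwise have judged suitable, no longer qualifies.

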1 BACKGROUND

1.1 Study Disease: Epithelial Ovarian, Fallopian Tube, or Peritoneal Cancer

Ovarian cancer is the leading cause of death from gynecologic malignancies [2]. More than 23,000 cases occur annually in the United States, and 14,000 women can be expected to succumb to the disease [3]. Despite advances in surgery, and chemotherapy over the past 20 years, only modest progress has been made in improving the time to disease progression [4, 5], and the overall survival for patients with ovarian cancer has not changed significantly. Although the majority of women with advanced stage ovarian cancer respond to first-line chemotherapy, most of these responses are not durable and more than 70% of patients die of recurrent disease within 5 years of diagnosis. By contrast, patients with early stage ovarian cancer have excellent prognosis with currently available treatment modalities. The poor survival in advanced disease is due both to late diagnosis and lack of effective second-line cytotoxic therapy for the majority of patients who relapse following initial clinical complete response to platinum-based chemotherapy. The inability to “cure” ovarian cancer is attributed to intrinsic or acquired resistance to drug therapy which is combated with high-dose chemotherapeutic regimens complicated by significant drug related morbidity and mortality. Moreover, effective strategy for the prevention of recurrence in complete responders is lacking. Therefore, new treatment modalities and paradigms are needed before a significant impact can be expected in the prognosis of women diagnosed with epithelial ovarian cancer. Fallopian tube and primary peritoneal cancers are clinically and biologically similar to ovarian cancer, and are treated in the same fashion.

1.2 NY-ESO-1 as a Target for Immunotherapy

There is increasing evidence that the immune system has the ability to recognize tumor-associated antigens expressed in human malignancies and to induce antigen-specific humoral and cellular immune responses to these targets. Importantly, evidence from correlative human studies indicate that the presence of tumor-infiltrating lymphocytes may be associated with improved clinical outcome in several human cancers, including ovarian, melanoma, colon, gastric, liver, brain, lungs, kidney and prostate cancers. In addition, encouraging results from large-scale clinical trials of immune system-provoking therapies [1-4] have re-kindled the promise of harnessing the power of the immune system to attack cancers. Therefore, the development of strategies to enhance the potential of tumor antigen-specific CD8+ T cells and CD4+ T cells is urgently needed for extending remission rates in several cancer types. In this regard, cancer-testis antigens, a unique class of antigens that demonstrate high levels of expression in adult male germ cells but generally not in other normal adult tissues and aberrant expression in a variable proportion of a wide range of different cancer types, are promising candidates for immunotherapy. Among cancer-testis antigens, NY-ESO-1 is one of the most spontaneously immunogenic tumor antigens described so far [5, 6]. The NCI antigen prioritization panel has recently ranked NY-ESO-1 in the top 10 antigens for further development of human cancer vaccines [7].

The NY-ESO-1 antigen was initially identified by serological analysis of recombinant cDNA expression libraries (SEREX), using tumor mRNA and autologous serum from a patient with squamous cell carcinoma of the esophagus. The full-length NY-ESO-1 cDNA was cloned, encoding a protein of 180 amino acids [5]. The function of this protein is unknown. The gene

encoding NY-ESO-1 has been mapped to chromosome Xq28 [5]. A gene LAGE-1, encoding an antigen closely related to NY-ESO-1, has also been mapped to chromosome Xq28 [8].

NY-ESO-1 showed restricted mRNA expression in normal tissues, with high-level mRNA expression found only in the germ line cells in testis [5, 9]. Reverse transcription-polymerase chain reaction (RT-PCR) analysis showed NY-ESO-1 mRNA expression in a variable proportion of a wide array of human cancers, including melanoma, breast cancer, prostate cancer, lung cancer, hepatocellular carcinoma, ovarian cancer, thyroid cancer and bladder cancer [9]. Expression of LAGE-1 parallels the expression of NY-ESO-1 in most cases [8]. The pattern of NY-ESO-1 and LAGE-1 expression indicates that NY-ESO-1 family belongs to a growing family of immunogenic testicular antigens that are aberrantly expressed in a wide range of human cancers. These antigens, initially detected by either cytotoxic T cells (MAGE, BAGE, GAGE-1) or antibodies [HOM-MEL-40 (SSX2), NY-ESO-1], represent a pool of antigenic targets for cancer vaccination [10]. The expression of these genes in many different types of cancer suggests that immunization against the antigens encoded by these genes could be applied to a large proportion of cancer patients.

NY-ESO-1 has 2 characteristics that make it a viable candidate as a tumor vaccine; [1] testis-restricted expression in normal tissues and; [2] its immunogenicity. The first characteristic also applies to MAGE and other genes with a similar expression pattern (see above). A serological survey has shown that patients with melanoma, ovarian cancer, lung cancer, or breast cancer produced antibodies against NY-ESO-1 more often (19 of 209) than antibodies against MAGE-1 (3 of 209) or MAGE-3 (2 of 209). Antibodies were not detected in 70 healthy blood donors [11]. This is evidence for NY-ESO-1 immunogenicity in patients with cancer, supporting the expectation that immunity can be enhanced or induced by vaccination.

